4.1. Patient accounting

Details of participants who are randomized, those who withdraw from the study after randomization and those who are lost to follow-up will be summarized in a CONSORT flow diagram. The number (%) of participants attending scheduled follow-up visits will be reported.

4.2. Description of study population

Participants in each intervention group, and in each site, will be described with respect to baseline characteristics. The description will be in terms of medians/means and quartiles/standard deviations for continuous characteristics and using counts and

percentages for categorical characteristics. The clinical importance of any imbalance will be noted though statistical tests of significance will not be undertaken.

5. Description of patient populations and outcomes

5.1. Patient populations

We will analyse the primary outcome both using Intention-to-Treat and Per-Protocol approaches, with Per-Protocol as primary approach. In the Intention-to-Treat analysis, all participants will be analysed according to their randomized allocation, even in case they receive another intervention, show protocol violations, or are lost to follow-up. In the per-protocol analysis only participants who receive intervention as planned, and follow the protocol as planned are included. For the safety analysis, all patients are included in the intervention group they actually received (all-patients-treated approach).

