Over 4 FU visits, this yields an average of 0.72 diagnoses per subject. Using a Poisson regression model with $\log(\text{number of visits})$ as offset, the 95% confidence interval of the log ratio (no screening vs. screening) is calculated. The 'no screening' arm is considered to be non-inferior if there is an increase of maximal 25% in number of diagnoses (i.e. increase of an average of 0.72 to 0.90 per 4 visits). The 'no screening' arm is proven to be non-inferior if the upper limit of the 95% confidence interval is lower than $\log(1.25)$. The required sample size to detect non-inferiority of the 'no screening' arm is calculated by simulation, assuming no difference between arms.

Assuming that 95% of the participants will have data on all 4 visits, and 5% will have data on only 3 visits, the required sample size to obtain 80% power is 912. Assuming an additional 10% drop out rate we will need to enroll 1014 participants.

The current number of PrEP participants at the ITM/HSP/EH/CHU/UZG is 803/739/290/260/240, respectively. At all 5 centres this number is increasing by approximately 20% per year. 99.7% of these individuals are MSM and over the age of 18. We estimate that 80% of the 2332 PrEP participants in these five centres will agree to participate. This number (n=1866) exceeds the number we need to enroll in the study (n=1014). By the commencement of the study (begin 2020) we estimate we will have 1518/886/464/314/298 individuals in the PrEP cohorts at the ITM/HSP/EH/CHU/UZG whom we will be able to screen for participation.

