11.3.2 Primary outcome analysis

We will analyse the primary outcome both using Intention-to-Treat and Per-Protocol approaches, with Per-Protocol as primary approach. In the Intention-to-Treat analysis, all participants will be analysed according to their randomized allocation, even in case they receive another intervention, show protocol violations prior to or during the study, or are lost-to follow. In the per-protocol analysis only participants who receive intervention as planned, and follow the protocol as planned

are included. If the person urgently requires knowing if they are infected with Ng/Ct or not this will be done by repeat testing for these infections. If this test is positive for Ng/Ct then this will be counted as an intervisit infection in the final analysis. In each arm, the incidence of Ng plus Ct will be estimated together with 95% confidence interval. Estimates will be based on a Poisson regression model with number of diagnoses as dependent variable, arm as independent variable, log(number of visits) as offset and a random intercept for site. This model will also provide an estimate of the log incidence rate ratio (no screening versus screening), together with 95% confidence interval. The 'no screening' arm is proven to be non-inferior if the upper limit of the 95% confidence interval is lower than log(1.25).

Visits with missing data on the diagnosis of Ng or Ct, will be excluded from the calculation of the incidence rate (excluded both from numerator and denominator).

Subgroup analysis:

We will conduct a prespecified sensitivity analysis to assess the incidence of Ng plus Ct in screening vs. non-screening arms ***in participants with lower-risk behavior***. An individual with lower-risk behavior is defined a priori as those individuals who report 4 or fewer partners per 3-month period in all 5 relevant 3 month periods. These periods are the 3-months prior to study enrollment as well as the four 3 month periods during study follow up). The analysis will be analogous to the analysis of the primary objective, but restricted to participants with lower-risk behavior.

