5.1.2. Per protocol (PP) analysis

In the per-protocol analysis only participants who receive intervention as planned, and follow the protocol as planned are included.

In Table 1 the protocol violations are classified as minor and major where minor violations can be included in the PP analysis population and major violations are excluded.

Table 1: The protocol violations classified as minor or major violation

Protocol Violation	Major/Minor Violation	Comments
Inclusion criteria		
1. Able and willing to provide informed consent	Major	
2. Men (born as males) and transwomen aged 18 or more	Major	
3. Has had sex with another man in the last 12 months	Major	
4. Enrolled in Belgian PrEP program at ITM/HSP/EH/CHU/UZG with approval for TDF/FTC (Tenofovir disoproxil fumarate/Emtricitabine) reimbursement from a Belgian Medical Aid	Major	
5. Willing to comply with the study procedures and to attend the clinic for the 3-monthly visits	Major	
Exclusion criteria		
1. Enrolment in another interventional trial	Major	
2. Tests HIV-positive at screening	Major	
3. Symptoms of proctitis or urethritis	Major	
Treatment violations		
1. Not following the randomized intervention (incl. participants who receive test results)	Major	
Follow-up violations		
1. Fewer than three scheduled follow-up visits with Ng/Ct result available	Major	

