Interim analyses are planned at two time points: once 50% and 100% of all study recruits have passed their 6 month visit. For the first interim analysis, data is used of the first 507 enrolled participants (i.e. ordered by randomization date) until 6 months follow-up. For the second analysis, data is used of all enrolled participants until 6 months follow-up. The goal of the interim analyses (at both time points) is to estimate the incidence rate ratio of symptomatic Ng plus CT. Estimates will be based on a Poisson regression model (or a negative binomial regression model if there is overdispersion) with number of symptomatic diagnoses as dependent variable, arm and hospital as independent variables and log(number of visits) as offset. This model will provide estimates of the incidence rate in each arm and the incidence rate ratio (no screening versus screening), together with 95% confidence interval. Visits with missing data on the diagnosis of Ng or Ct, will be excluded from the calculation of the incidence rate (excluded both from numerator and denominator).

7. Analysis of main efficacy outcomes: Incidence of Ng plus Ct

In each arm, the incidence of Ng plus Ct will be estimated together with 95% confidence interval. Estimates will be based on a Poisson regression model (or a negative binomial regression model if there is overdispersion) with number of diagnoses as dependent variable, arm and hospital as independent variables, and log(number of visits) as offset. This model will also provide an estimate of the log incidence rate ratio (no screening versus screening), together with 95% confidence interval. The 'no screening' arm is proven to be non-inferior if the upper limit of the 95% confidence interval is lower than $\log(1.25)$.

Visits with missing data on the diagnosis of Ng or Ct, will be excluded from the calculation of the incidence rate (excluded both from numerator and denominator).

In a sensitivity analysis, the numerator of the primary endpoint will only include diagnoses if there was a negative test result at the prior visit.

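### Non-inferiority can be declared on the per-protocol result when the analysis by randomised arm misses the 1.25 margin, because no rule covers disagreement between the two

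*SAP*

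**What the plan says.** SAP 5.1 states: "We will analyse the primary outcome both using Intention-to-Treat and Per-Protocol approaches, with Per-Protocol as primary approach". Protocol 11.3.2 says the same. The rule follows in Protocol 11.3.2 and SAP section 7: the no-screening arm "is proven to be non-inferior if the upper limit of the 95% confidence interval is lower than" log(1.25). It names no analysis set and does not say what is concluded if the two analyses disagree.

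SAP 5.1.2, Table 1 lists the major violations that remove a man from the per-protocol set. Two arise after randomisation:

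- "Fewer than three scheduled follow-up visits with Ng/Ct result available". SAP section 3 widens this, because an out-of-window scheduled visit counts as not done.
- Not following the randomised intervention, which the table says includes participants who are given test results.

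The SAP's ITT set (5.1.1) keeps everyone in the randomised arm but requires at least one follow-up visit. Protocol 8.4 describes the trial as unblinded.

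**The concern.** With per-protocol primary and no condition on ITT, the rule is met by a per-protocol pass whatever ITT shows. The conclusion could then rest on a set formed by events after randomisation.

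The clause on test results makes this more than a general worry. Receiving results is the assigned strategy in the screening arm, so that clause can only remove men from the no-screening arm. Under the protocol, men in that arm can learn results when they attend with symptoms (8.7), may be tested after partner notification (8.7), and can have repeat testing when they urgently need to know (8.5). Such men are plausibly more likely to be infected. Removing them lowers the no-screening rate and favours non-inferiority.

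The reach of the clause is also unclear. Protocol 8.5 keeps urgent testers in the study and SAP 5.2 counts their positive tests as infections between visits, yet Table 1 read literally would drop them from the per-protocol set.

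The stakes are practical. Section 2 of the protocol says that if screening is not found to reduce incidence, the investigators will recommend to the national consortium that screening of PrEP users and other MSM cease.

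**Working it through.** **Inputs from Protocol 11.1 and 8.3.** The margin is met "if there is an increase of maximal 25% in number of diagnoses". Screening-arm mean 0.72 diagnoses over 4 visits; true ratio 1; 95% of men with 4 visits and 5% with 3 (mean 0.95 × 4 + 0.05 × 3 = 3.95); allocation 1:1; two-sided 95% interval; 912 evaluable for 80% power; 10% dropout; 1014 enrolled.

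**Step 1: reproduce the plan's figure.** For a Poisson log rate ratio, n per arm = 2(z₀.₉₇₅ + z₀.₈₀)² / (μ × log(1.25)²).

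- With μ = 0.72 × 3.95/4 = 0.711: 2 × 7.849 / (0.711 × 0.0498) gives 444 per arm, N = 888.
- With the mean from the protocol's table (0.79 × 0.15 + 0.18 × 0.28 + 0.03 × 0.34 = 0.1791 per visit, 0.7164 over four): 446 per arm, N = 892.
- Simulating from that table at N = 912 gives 79.7% power. The table implies mild overdispersion (about 1.06), which explains the shortfall from the formula's 81%.
- 912/0.90 = 1013.3, so 1014 for equal arms.

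The design reproduces.

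**Step 2: how far the two sets differ through dropout alone.** Assume the 10% who drop out have 0, 1 or 2 usable visits with equal chance (mean 1). Visits per randomised man are 0.9 × 3.95 = 3.555 in per-protocol and 3.555 + 0.1 × 1 = 3.655 in ITT. Per-protocol holds 3.555/3.655 = 97.3% of the visits, so the two estimates correlate at about √0.973 = 0.99.

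**Step 3: simulate both analyses.** 507 per arm, a plain Poisson interval without the hospital term, 6,000 trials per row. Assumed scenarios:

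- A: dropout only, at random.
- B, C: as A, with a further random 5% or 10% of the no-screening arm excluded from per-protocol.
- D, E: as B and C, but men ever diagnosed are three times as likely to be excluded.

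| Scenario | True ratio | ITT passes | PP passes | Both pass | PP passes, ITT fails |
|---|---|---|---|---|---|
| A | 1.0 | 81.2% | 80.1% | 78.7% | 1.4% |
| A | 1.1 | 39.8% | 39.4% | 37.1% | 2.2% |
| A | 1.25 | 2.6% | 2.5% | 2.1% | 0.4% |
| B | 1.0 | 81.0% | 78.5% | 76.8% | 1.7% |
| B | 1.1 | 41.1% | 39.3% | 36.8% | 2.6% |
| B | 1.25 | 2.7% | 2.4% | 2.1% | 0.4% |
| C | 1.0 | 80.8% | 77.9% | 76.2% | 1.6% |
| C | 1.1 | 39.4% | 37.2% | 34.3% | 2.9% |
| C | 1.25 | 2.8% | 2.6% | 2.1% | 0.5% |
| D | 1.0 | 80.5% | 86.9% | 80.2% | 6.7% |
| D | 1.1 | 39.3% | 49.9% | 38.7% | 11.2% |
| D | 1.25 | 2.8% | 5.4% | 2.6% | 2.8% |
| E | 1.0 | 80.2% | 91.8% | 80.2% | 11.6% |
| E | 1.1 | 39.5% | 61.9% | 39.4% | 22.5% |
| E | 1.25 | 2.8% | 9.1% | 2.8% | 6.2% |

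At a true ratio of 1.25, the per-protocol estimate averages 1.224 in D and 1.195 in E: selection alone moves it inside the margin.

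Simulation error is about √(0.8 × 0.2/6000) = 0.5 points near 80% and √(0.025 × 0.975/6000) = 0.2 points near 2.5%. Repeating every row with 20,000 trials gave the same picture; joint power at a true ratio of 1 was 78.8% in A, 77.6% in B and 76.2% in C.

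**The case against.** Per-protocol is a recognised choice in a non-inferiority trial. Testing outside the study, urgent repeat tests and testing after partner notification can all blur the contrast between arms. That pulls ITT towards 1, which itself favours non-inferiority. This argument stands: naming per-protocol as primary is not the defect.

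A reader might infer that the plan ignores ITT. The documents do not support that. No sentence sets ITT aside, it is run on the primary outcome, and a disagreement would be visible. What is missing is what that disagreement would mean for the conclusion.

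A reader might also infer that the planned 10% dropout will itself drive the two analyses apart. It will not. The protocol does not place those men outside per-protocol but inside ITT, the SAP's ITT set also omits men with no follow-up visit, and step 2 shows near-identical estimates under dropout alone. A wide gap between the upper limits would be unusual if exclusions were random.

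Finally, the documents give no rate for exclusions due to test results and do not say how selective they would be. The 5–10% and threefold figures are scenarios, not forecasts.

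**Conclusion.** The gap is real: as written, non-inferiority can be declared while the analysis by randomised arm misses 1.25. Its size depends on how selective the exclusions are.

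- With dropout alone, at random, it matters little: discordance in favour of per-protocol is 0.4–2.2%, or at most 2.9% with a further random 5–10% of the no-screening arm excluded.
- Under the assumed informative exclusions, discordance is about 3–22%, and the per-protocol false-positive rate at a true ratio of 1.25 is about 5–9%, against 2.6–2.8% for ITT across all scenarios.

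These figures rest on the plan's event rates and dropout, an assumed spread of visits among dropouts, and a Poisson interval without the hospital term. This is a cheap improvement to the decision rule. It does not make the design unsound.

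**What to change.** In SAP section 7 and Protocol 11.3.2, add:

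> No screening is declared non-inferior only if the upper 95% limit is below 1.25 in both the per-protocol and the ITT analysis; if they disagree, non-inferiority is not concluded.

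No alpha adjustment is needed, because both must pass. In the informative scenarios at a true ratio of 1.25, the joint rule gives 2.6–2.8%.

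The cost is one sentence in each document and about 1 to 2 points of power under the plan's dropout assumption (80.1% to 78.7%). Joint power is about 76–78% if a further random 5–10% of the no-screening arm is excluded.

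While Table 1 is open, it would help to state whether its clause on test results covers men tested at unscheduled visits, since Protocol 8.5 and SAP 5.2 keep urgent testers and their infections in the analysis. SAP section 1 has the plan finalised before database lock, so the rule should be in place by then.

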5.1.1. Intention to treat (ITT) analysis

In the Intention-to-Treat analysis, all participants will be analysed according to their randomized allocation, even in case they receive another intervention, show protocol violations prior to or during the study, or are lost to follow-up. The Intention-to-Treat analysis will include all randomized participants with at least one follow-up visit.

5.1.2. Per protocol (PP) analysis

In the per-protocol analysis only participants who receive intervention as planned, and follow the protocol as planned are included.

In Table 1 the protocol violations are classified as minor and major where minor violations can be included in the PP analysis population and major violations are excluded.

Table 1: The protocol violations classified as minor or major violation

Protocol Violation	Major/Minor Violation	Comments
Inclusion criteria		
1. Able and willing to provide informed consent	Major	
2. Men (born as males) and transwomen aged 18 or more	Major	
3. Has had sex with another man in the last 12 months	Major	
4. Enrolled in Belgian PrEP program at ITM/HSP/EH/CHU/UZG with approval for TDF/FTC (Tenofovir disoproxil fumarate/Emtricitabine) reimbursement from a Belgian Medical Aid	Major	
5. Willing to comply with the study procedures and to attend the clinic for the 3-monthly visits	Major	
Exclusion criteria		
1. Enrolment in another interventional trial	Major	
2. Tests HIV-positive at screening	Major	
3. Symptoms of proctitis or urethritis	Major	
Treatment violations		
1. Not following the randomized intervention (incl. participants who receive test results)	Major	
Follow-up violations		
1. Fewer than three scheduled follow-up visits with Ng/Ct result available	Major	

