4.3 Endpoints

4.3.1 Primary endpoint

Incidence of Ng plus Ct detected at any site whilst individuals are screened vs. not screened.

Numerators: Cumulative number of diagnoses of Ng plus Ct in 12 months in screening/non-screening arms. Each participant can only contribute one diagnosis of Ct and one diagnosis of Ng per (scheduled or unscheduled) visit - regardless of number of sites infected. Thus each participant can contribute up to 2 diagnoses (Ct/Ng) at each (scheduled or unscheduled) visit. The numerator includes laboratory-confirmed diagnoses made between scheduled visits, performed inside or outside of the study.

Denominators: Number of scheduled study visits with available results for the diagnosis of Ng/Ct. The denominator does not include unscheduled visits^a.

The diagnosis of Ng and Ct will be made via nucleic acid amplification testing (NAAT) performed on rectal and pharyngeal swabs and urine.

In the primary analysis, the primary endpoint (as described above) includes all Ng/Ct diagnoses. Hence it is implicitly assumed that every diagnosis is a new infection. It is however possible that an Ng/Ct infection detected at the 3 to 12 month visit in the non-screening arm is simply a non-resolved infection from the prior visit (see Figure 5)^b. This could spuriously increase the measured incidence in the non-screening group. Because

^a The rationale for this definition of the denominator is to, as closely as possible, reflect time at risk of testing Ng/Ct positive. If an individual misses one of their 4 study follow up visits then this reduces their probability of being diagnosed with Ng or Ct by one quarter (assuming no other relevant variables change). Our denominator definition takes this into account by only including study visits where we have results of Ng/Ct testing. Unscheduled visits are not included as these make up a very small proportion of all visits and could be considered to bias the time at risk estimate.

[figure not shown]
^b Given the natural rate of clearance of Ng and Ct from each site, this probability is very low

this risk only applies to the non-screening arm it results in a bias towards exaggerating the effect of screening on incidence. As such if our study finds that non-screening is non-inferior to screening this finding could not be explained by this bias. In a sensitivity analysis, the numerator of the primary endpoint will only include diagnoses if there was a negative test result at the prior visit.

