11.3.4 Procedure(s) to account for missing or spurious data

PrEP recipients are required to attend follow up 3 monthly and adherence rates with this requirement are high. This is in part related to the fact that they need to attend 3-monthly to receive their prescriptions for the next 3 months. In the study we will allow study visits to be from one week before to 6 weeks after this 3-month duration. This will decrease the proportion with missed visits.

Study participants who miss their follow up visits (defined as more than 6 weeks after their 3 month follow up visit) will be contacted to attend as soon as possible. If they miss a visit, the reason for this will be recorded in the source document and eCRF.

Missed visits will be excluded from the denominator of incidence.

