Cost of culture & sensitivity testing for positive Ng molecular tests	Possible reduced transmission of Ng/Ct (population level benefit)
Consultation fee initial screening visit	Screening results in individuals with higher risk behaviour attending follow up regularly
Consultation fee visit to receive treatment	
Follow up visit to assess test of cure (Ng)	
Price of antimicrobial therapy	
Indirect	
Time to attend consultations	
Adverse effects of high level of antimicrobial consumption on individual's health including microbiome	
Adverse effects of high level of antimicrobial consumption on selection of antimicrobial resistance (individual and population level cost)	
Certificate of health effect may result in increased risk behaviour	

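### The primary per-protocol set drops men with fewer than three scheduled Ng/Ct results; if attendance depends on arm and infection risk, this favours non-inferiority, ITT has no stated deciding role, and missed visits are not explored

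*SAP*

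**What the plan says.** SAP 5.1 analyses the primary outcome by both ITT and per-protocol, "with Per-Protocol as primary approach". SAP 5.1.2 states that "minor violations can be included in the PP analysis population and major violations are excluded", and Table 1 there classes "Fewer than three scheduled follow-up visits with Ng/Ct result available" as major. SAP section 3 enlarges that group, because a scheduled visit made outside its window counts as not done. SAP 5.1.1 defines ITT as all randomised men with at least one follow-up visit.

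The per-protocol definition in protocol 11.3.2 contains no visit count. Protocol 8.12.1 says that data from men who stop trial procedures are used up to the point of withdrawal.

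Missed visits are already dealt with in the endpoint. Protocol 11.3.4: "Missed visits will be excluded from the denominator of incidence". The footnote to protocol 4.3.1: "Our denominator definition takes this into account by only including study visits where we have results of Ng/Ct testing". The model in SAP section 7 carries log(number of visits) as offset.

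On attendance, Table 3 in protocol 11.4 lists as a benefit of screening: "Screening results in individuals with higher risk behaviour attending follow up regularly". The other two benefits in that table are qualified as possible; this one is not. Protocol 11.3.4 says that adherence to visits is high: "This is in part related to the fact that they need to attend 3-monthly to receive their prescriptions for the next 3 months".

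For the sample size, protocol 11.1 states: "Assuming an additional 10% drop out rate we will need to enroll 1014 participants".

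**The concern.** The question is the Ng/Ct incidence with and without screening among men on PrEP. The primary analysis answers it for men who supplied at least three in-window results. The offset corrects for how many visits a man contributed. It does not correct for which men or which visits are missing.

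If screening keeps higher-risk men attending, being excluded depends on arm and on infection risk together. The no-screening arm then loses more of its high-incidence men, its rate falls, and the ratio moves towards a non-inferior result. Protocol sections 2 and 11.4 would use such a result to recommend stopping screening.

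The plan's argument that bias could not explain a non-inferior result covers only unresolved infections carried over between visits. The planned sensitivity analysis, which requires a negative prior test, addresses that carry-over and not attendance.

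**Working it through.** **1. Reproduce the plan's figure.** Inputs from protocol 11.1: baseline mix 79/18/3%; 0.15, 0.28 and 0.34 diagnoses per visit for 0, 1 and 2 baseline diagnoses; margin 1.25; two-sided 95% interval; 80% power; 95% of men with 4 visits and 5% with 3.

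- Mean per visit: 0.79×0.15 + 0.18×0.28 + 0.03×0.34 = 0.179, or 0.72 over four visits, as stated.
- Events per arm: 2(1.96+0.84)²/ln(1.25)² = 315.
- Visits per man: 0.95×4 + 0.05×3 = 3.95. Men per arm: 315/(0.179×3.95) = 446, or 892 in total, against 912 by the protocol's simulation. Simulating 456 per arm gives 80.4% power.
- 912/0.90 gives 1014.

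**2. Risk difference in the protocol's rates.** Baseline-positive men are 21% of the total. Their rate is (0.18×0.28 + 0.03×0.34)/0.21 = 0.289 per visit, 1.61 times the mean.

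**3. Effect of risk-related loss.** Assumptions: 10% of each arm falls below three results (the plan's drop-out figure); screening-arm loss is random; in the no-screening arm, baseline-positive men are k times as likely to be lost.

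- Share of the lost who are baseline-positive: q = 0.21k/(0.21k + 0.79).
- Retained rate: [0.289(0.21 − 0.1q) + 0.15(0.9 − 0.21 + 0.1q)]/0.9. Dividing by 0.179 gives the factor f on the rate ratio.
- False non-inferiority at a true ratio of 1.25 is about Φ(−1.96 + |ln f|/SE), with SE about 0.075.

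| k | q | f | share of ln(1.25) | false non-inferiority |
|---|---|---|---|---|
| 2 | 0.347 | 0.988 | 5% | 3.6% |
| 3 | 0.444 | 0.980 | 9% | 4.6% |
| 4 | 0.515 | 0.974 | 12% | 5.4% |

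Simulating the same scenarios gives 3.5–5.1% with the three-visit rule and 3.3–4.2% when everyone with at least one result is kept. Much of the bias therefore comes from the missed visits and remains without the rule.

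**4. Stronger heterogeneity.** Let individual rates vary (gamma) and let loss be proportional to a man's rate: CV² = (φ − 1)/0.72 and f = (1 − 0.1(1 + CV²))/0.9.

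- φ = 1.2: f = 0.969; about 5% false non-inferiority.
- φ = 1.35: f = 0.946; 9.3% with the rule, 6.4% keeping everyone with one result.

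The protocol's table implies a smaller φ. The variance of the four-visit total is 4×0.1769 (within group) + 16×0.00328 (between groups) = 0.760, and 0.760/0.716 = 1.06. At that value f = 0.991.

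**5. Boundary cases (507 per arm, true ratio 1.25).**

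- Random 10% loss in both arms: ratio 1.25, false non-inferiority 2.6%.
- The same 10% high-risk loss in both arms: 1.25 and 2.7%.
- Every lost no-screening man baseline-positive: 5% lost gives 6.9% per-protocol and 4.8% ITT; 10% lost gives 15–16% and 8–9%. The last is a near-worst case.

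**6. Power without the rule.** At a true ratio of 1 with 10% random early loss in both arms, power is 82.1% keeping everyone with one result, against 80.0% with the rule.

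**The case against.** Four points count against pressing this too far.

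- **ITT is planned.** It keeps most of the men whom the rule removes, with the same offset, so comparing it with per-protocol shows the effect of the three-visit cut. A reader might infer that nothing in the plan reveals dependence on attendance; SAP 5.1.1 does not support that. What stands is narrower. ITT has no stated role in the decision, also includes men who did not follow their allocation, omits men with no follow-up visit, and models nothing for missed visits.
- **The direction is not settled.** A reader might infer that the no-screening arm will lose its high-risk men. Table 3 concerns expected effects of screening as a policy, in the economic section, not trial attendance. Visits and sampling are identical in both arms, and prescriptions drive attendance in both. Protocol 8.7 also describes 3-monthly follow-up with extra returns for treatment as onerous, a burden that would fall more on high-incidence men in the screening arm. Carry-over positives push the ratio upwards. These points make the bias possible rather than established. Participants can, however, work out their arm (protocol 8.4), so attendance that differs by arm cannot be ruled out.
- **The rule has some use.** Out-of-window positives count as unscheduled diagnoses, so they enter the numerator only; a minimum visit count limits their weight. Men with only early results, when care has barely differed between arms, also pull the ratio towards 1. Both points stand and bear on the choice of fix.
- **Minimum attendance is an ordinary per-protocol criterion.** That is true, but here the set it defines is primary.

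**Conclusion.** The concern holds as a conditional one. The primary set discards usable data by a criterion that may be related to arm and outcome; the offset corrects for exposure and not for selection. With 10% loss, the protocol's own rates and a 2- to 4-fold higher loss of baseline-positive men in the no-screening arm only, the ratio is multiplied by about 0.99 to 0.97 and false non-inferiority is about 3.5–5% instead of 2.5%.

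A reader might take about 9% as the expected error. Under loss proportional to individual rate, that needs an assumed overdispersion of 1.35, against 1.06 implied by the protocol's table. The 15–16% figure needs every lost man in the no-screening arm to be baseline-positive. The documents give no loss by arm and no risk profile of the men lost, so they support neither as a forecast. Loss that is unrelated to risk, or equal in type and size in both arms, produces no bias.

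Since removing the visit-count rule leaves much of the bias in place, the larger gap is the lack of a missed-visit analysis and of a stated role for ITT.

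**What to change.** 1. In SAP section 7, state that non-inferiority is concluded only if the upper limit is below 1.25 in both the per-protocol and ITT sets. Alternatively, class the follow-up row of Table 1 as minor, so that otherwise compliant men with at least one scheduled result stay in.
2. In SAP 7.2b, add one sensitivity analysis of the primary rate ratio. Multiply impute missed scheduled visits within arm from baseline partner number, prior STIs and earlier study results. Then raise the imputed no-screening rate stepwise (for example ×1.25, ×1.5, ×2) and report the factor at which the upper limit reaches 1.25.
3. Report exclusions and missed visits by arm and baseline risk.

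The cost is SAP wording and modest extra analysis of data already collected, with no new visits or participants. Requiring both sets makes the conclusion somewhat stricter.

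If the row is downgraded instead, the added data are small. About 101 men (10% of 1014) with 0 to 2 results, averaging one each, add about 100 visits to 912×3.95 ≈ 3,600, or 3%. The dilution from early visits and the weight of out-of-window positives in men with few scheduled visits should then be checked.
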